2.12 Biomarkers

Not applicable.

2.14 Interim analysis

The database of this study will be locked twice, first after the end of Treatment Period 1 (Week 16) and again after the end of Treatment Period 2 (Week 52). Data analyses will follow after database lock at Week 16. The main analysis for the primary objective will be done at Week 16. As Week 16 is the primary analysis time point, no adjustment to the significance level of 0.05 will be made.

3 Sample size calculation

The sample size was calculated based on the primary efficacy variable (i.e., ACR20 response) for the primary comparison (i.e., secukinumab 300 mg versus placebo). ACR20 response rates of 50% for secukinumab 300 mg and 20% for placebo (corresponding to an Odds ratio of 4) at Week 16 were assumed, based on results from AIN457F2312 (FUTURE 2) study. Using a continuity-corrected chi-squared test, an allocation ratio of 2:1, a two-sided significance level of 0.05, and a power of 0.90, approximately 88 patients in secukinumab 300 mg group and 44 patients in placebo group will be needed.

Assuming a loss to follow-up rate of 10% and a 2:2:1 allocation ratio (secukinumab 300 mg: secukinumab 150 mg: placebo), the total number of randomized patients will be approximately 250 (100 on secukinumab 300 mg, 100 on secukinumab 150 mg, and 50 on placebo).

The sample size estimation was done using query Advisor 7.0.

4 Change to protocol specified analyses

Not applicable.

5 Appendix

This section will be used later for drafting CSR Appendix 16.1.9.

5.1 Imputation rules

5.1.1 Study drug

Not applicable

5.1.2 AE date imputation

The following table explains the notation used in the logic matrix. Please note that missing start dates will not be imputed.

	Day	Month	Year
Partial Adverse Event Start Date	Not used	MON	YYYY
Treatment Start Date (TRTSTD)	Not used	TRTM	TRTY

The following matrix explains the logic behind the imputation.

	MON MISSIN	MON < TRTM	MON = TRTM	MON > TRTM
YYYY Missin	NC Uncertain	N C	N C	N C
YYYY < TRTY	(D) Before Treatment Start	(C)	(C)	(C)
YYYY = TRTY	(B) Uncertain	(C) Defere Treatment	(A)	(A)
YYYY > TRTY	(E) After Treatment Start	(A) After Treatment	(A)	(A)

The following table is the legend to the logic matrix.

If AE end date is complete and AE end date < Treatment start date or AE end date is partial and AE imputed end date < Treatment start date, then AE start reference = min (informed consent date, earliest visit date from SV) Else if AE end date is partial, AE end date > = Treatment start date or AE is ongoing, then AE start reference = treatment start date.

Time imputation

Before AE start reference	Partial date indicates AE start date prior to AE start	
After AE start reference	Partial date indicates AE start date after AE start	
Uncertain	Partial date insufficient to determine relationship of AE start date to AE start	
Imputation Calculation	-	
NC/Blank	No convention	
(A)	MAX(01MONYYYY, AE start reference+1 day)	
(B)	AE start reference+1	
(C)	15MONYYYY	
(D)	01JULYYYY	
(E)	01JANYYYY	
Complete date	No date imputation	If time is captured for the study Case1: if AE start date is not equal to AE start reference then do the following:

Time imputation
If minutes missing then AESTMF = M and time is imputed to hh: 00
If minutes missing then AESTMF = H and time is imputed to 00:00
Case2: if AE start date = AE start reference then AESTMF = H and time is imputed to treatment start time + 1 hour

Adverse Event End Date Imputation

Imputed date = date part of original date, if complete date Imputed date = min (completion/discontinuation visit date, DEC 31, date of death), if

month is missing

Imputed date = min (completion/discontinuation visit date, last day of the month, date of death), if day is missing

Adverse Event End Time Imputation

If the AE end date is complete and time is captured in the study then:

Case 1. if AE end date is not equal to Treatment end date, then do the following: if minutes missing then time is imputed to be 00 if time missing then time is imputed.

if minutes missing then time is imputed to hh: 00 $\,$ if time missing then time is imputed to 00:00

Novartis	For business use only	Page 52
SAP		Secukinumab/AIN457FUS01

Case 2: if AE end date = Treatment end date then time is imputed to treatment end time If the AE end date is partial then end time is imputed to 00:00.

Imputed Date Flag

If year of the imputed date is not equal to YYYY then date flag = Yelse if month of the imputed date is not equal to MON then date flag = Melse if day of the imputed date is not equal to day of original date then date_flag = D else date flag = null

Imputed Time Flag

If hours of the imputed time is not equal to hours of original time then time flag = H else if minutes of the imputed time is not equal to minutes of original time then time flag = M

else time flag = null.

5.1.3 Concomitant medication date imputation

This algorithm is used when *event* is the partial start date of the concomitant medication. The following table explains the notation used in the logic matrix. Please note that **missing start dates** will not be imputed.

	Day		Year
Partial CM Start Date	Not used	MON	YYYY
Treatment Start Date (TRTSDT)	Not used	TRTM	TRTY

·	MON MISSING	MON < TRTM	MON = TRTM	MON > TRTM
YYYY	(C2)	(C1)	(C1)	(C1)
MISSING	Uncertain	Uncertain	Uncertain	Uncertain
YYYY < TRTY	(D)	(A)	(A)	(A)
	Before Treatment Start	Before Treatment Start	Before Treatment Start	Before Treatment Start
YYYY = TRTY	(C2)	(A)	(C1)	(B)
	Uncertain	Before Treatment Start	Uncertain	After Treatment Start
YYYY > TRTY	(E)	(B)	(B)	(B)
	After Treatment Start	After Treatment Start	After Treatment Start	After Treatment Start

The following matrix explains the logic behind the imputation.

The following table is the legend to the logic matrix.

Relationship	
Before Treatment Start	Partial date indicates CMD start date prior to Treatment Start Date
After Treatment Start	Partial date indicates CMD start date after Treatment Start Date
Uncertain	Partial date insufficient to determine relationship of CMD start date relative to Treatment Start Date
Imputation Calculation	
(A)	15MONYYYY

(B)	01MONYYYY
(C1 or C2)	IF relative reference start = before treatment start THEN TRTSDT-1
	ELSE IF relative reference start = ' ' THEN TRTSDT+1
(D)	01JULYYYY
(E)	01JANYYYY

Concomitant Medication End Date Imputation

If not ongoing then -Imputed date = date part of CMENDTC, if complete date Imputed date = min (completion/discontinuation visit date, DEC 31), if month is missing, (C2, D, E) Imputed date = min (completion/discontinuation visit date, last day of the Month), if day is missing. (A, B, C1)

Concomitant Medication Date Flag

If not a complete date then

Y - If year of the imputed date is not equal to YYYY else M - If month of the imputed date is not equal to MON else D.

5.1.3.1 Prior therapies date imputation

Same as above.

5.1.3.2 Post therapies date imputation

Same as above.

5.1.3.3 Other imputations

Same as above.

5.2 AEs coding/grading

Not applicable.

5.3 Laboratory parameters derivations

Not applicable.

5.4 Statistical models

5.4.1 Primary analysis

The primary analysis will be performed comparing treatments with respect to the primary

efficacy variable in a logistic regression model with treatment, methotrexate usage at baseline (yes, no), and body weight as explanatory variables.

Proc logistic data=aaa; Class TRT MTX/ param=glm; Model AVAL= TRT MTX weight; Lsmeans TRT / diff cl exp; Ods output diffs=lsm_diff; Run;

Logistic regression will be applied to response variables at each visit.

In cases where logistic regression doesn't converge, Fisher's exact test will be applied for comparisons between AIN457 doses. In this case, no odds ratios or confidence intervals will be estimated, but p-values may be calculated.

Proc freq data=aaa; Table TRT * AVAL / fisher; Where TRT in ("AIN457 xx mg" "Placebo"); Run;

In cases where separation is a concern, e.g. 0% response in one treatment (sub) group, an exact logistic regression model will be applied. Proc logistic data=aaa exactonly; Class TRT MTX / param=glm; Model AVAL = TRT MTX weight; Exact TRT / estimate;

Ods output exactoddsratio=exactoddsratio;

Run;

For supportive analysis using Cochran-Mantel-Haenszel (CMH) test to compare treatment adjusting methotrexate usage at baseline, the following code will be used.

proc freq data=aaa; tables TRT*MTX / cmh; run;

where AVAL= dependent variable TRT= Treatment MTX= Methotrexate usage at baseline Weight= body weight

Multiple Imputation

A multiple imputation will be performed based on MAR with treatment (3 treatment groups), methotrexate usage at baseline (yes, no), and body weight (in kg) as explanatory variables of primary efficacy variable (ACR20 response) for visits up to the primary time point (Week 16) using Markov Chain Monte Carlo (MCMC) method with EM algorithm.

Impute the missing values 100 times (NIMPUTE) with a seed=457<studycode> as shown below:

proc mi data= min= max= out=imp minmaxiter=10000000 nimpute=100 seed=457;

by trt;

var weight_base mtxuse_base var1_week1-var1_week16;

mcmc chain=multiple initial=em;

run;

Where var1 is the 1st component of ACR and this step will be repeated for every components of ACR, e.g., as follows:

proc mi data=imp min=<min of scale> max=<max of scale> out=imp2 minmaxiter=10000000 nimpute=100 seed=457;

by trt _imputation_; var weight_base mxtuse_basevar2_week1-var2_week16; mcmc chain=multiple initial=em;

run;

The score and ACR response can now be calculated based on the complete data. The response rate will be calculated for each imputation and then combined using Rubin's rules.

In order to calculate the response rate for each imputation, PROC FREQ will be used as follows.

Calculate binomial proportion and standard error for each imputation.

proc freq data=<ACR20>;

by trt visit _imputation_ ;

```
tables <response> / binomial (level=2 cl=wilson correct);
```

ods output BinomialProp=imp bpr;

run;

Transpose the dataset for subsequent use with PROC MIANALYZE.

proc transpose data=imp_bpr out=imp_trs(drop=_name_);

```
by trt visit _imputation_ ;
```

var nvalue1; id name1; idlabel label1; run;

```
Apply LOGIT transformation: y=log(p/(1-p)) and std. err. transformation: <new \ se> = se/(p*(1-p))
```

```
data logit;
set imp_trs(rename=(_bin_=p e_bin=se));
by trt visit _imputation_;
lmean=log(p/(1-p));
lse=se/(p*(1-p));
run;
```

The transformed binomial proportion estimates and standard errors are combined by applying Rubin's rules for multiple imputed data sets.

proc mianalyze data=logit; by trt visit ; modeleffects lmean; stderr lse; ods output ParameterEstimates=logitres; run;

The combined data should be transformed back using the following formula: p=1/(1+exp(-y)) data miexpres;

```
set logitres;
by trt visit ;
resti = 1/(1+exp(-estimate));
rlow = 1/(1+exp(-lclmean));
rupp = 1/(1+exp(-uclmean));
run;
```

Of note, sometimes all responses may be imputed to 0 or 1 at a given combination of response variable, treatment group and visit. Such cases should be considered separately. The combined final response rate would be the same as the original response but the 95% CI will be undefined.

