2.5.2 Statistical hypothesis, model, and method of analysis

Let π_i denote the probability of an ACR20 response at Week 16 for treatment group j, j = 0, 1, 2, where 0 corresponds to placebo, 1 corresponds to secukinumab 150 mg, and 2 corresponds to secukinumab 300 mg. Accordingly, $\pi_i/(1 - \pi_i)$ is the odds for treatment group j, j = 0, 1, 2.

The following null hypotheses (H_{01} and H_{02}) will be tested against their corresponding alternative hypotheses (H_{A1} and H_{A2}):

 $H_{01}: [\pi_1/(1-\pi_1)]/[\pi_0/(1-\pi_0)] \le 1$ versus $H_{A1}: [\pi_1/(1-\pi_1)]/[\pi_0/(1-\pi_0)] > 1$

H₀₂: $[\pi_2/(1-\pi_2)]/[\pi_0/(1-\pi_0)] \le 1$ versus H_{A2}: $[\pi_2/(1-\pi_2)]/[\pi_0/(1-\pi_0)] > 1$

The primary efficacy variable will be analyzed at Week 16 using a logistic regression model with treatment (3 treatment groups), methotrexate usage at baseline (yes, no), and body weight (in kg) as explanatory variables (Stokes, Davis, and Koch, 2012). The odds ratios for each dose of secukinumab versus placebo, 95% confidence intervals for the odds ratios, and p-values based on the fitted model will be reported. If the p-value for a dose of secukinumab versus placebo is < 0.05 and the corresponding odds ratio is greater than 1, statistical significance in favor of that dose of secukinumab is shown.

Methotrexate usage at baseline and body weight are assumed to have possible impact on the variable, so those will be included in the logistic regression model, even though the factors will not be used to stratify at randomization.

The primary variable will also be analyzed at each time point till Week 16 using the same model.

Number and percentages of ACR20 responders will be reported for each treatment group by visit in entire treatment period up to Week 52 using oberved data. Similar summary will be provided for ACR20 using non-responder imputation.

Number and percentages of ACR20 responders will be reported for each treatment group, concomitant methotrexate usage at baseline and by visit in entire treatment period up to Week 52. Similar summary will be provided for ACR20 using non-responder imputation.

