5.4.3 Secondary analysis

Categorical variables will be analyzed using the logistic model, using the code described above.

Continuous variables will be analyzed using an analysis of covariance (ANCOVA) model with treatment, baseline value, methotrexate usage at baseline (yes, no), and body weight as explanatory variables.

Proc mixed data=aaa order=internal; Class TRT MTX; Model change=TRT MTX BLV weight/ ddfm=kr; Lsmeans TRT/ cl diff; Contrast "sec300 vs plb" TRT 1 0 -1/ cl diff alpha=0.05; Contrast "sec150 vs plb" TRT 0 1 -1/ cl diff alpha=0.05; Run;

For supportive analysis using Cochran-Mantel-Haenszel (CMH) test to compare treatments adjusting for methotrexate usage at baseline, the same code will be used as described above.

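### The logistic code in SAP 5.4.1 names neither the event nor the control arm; on the coding the SAP's own code implies, it prints the odds ratio for non-response and contradicts the success rule

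*SAP*

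**What the plan says.** SAP 2.5.2 and Protocol 9.4.2 define the target as the probability of an ACR20 response at Week 16. They write the hypotheses as the odds of response on each dose over the odds on placebo. The direction of the odds ratio is part of the decision rule: "If the p-value for a dose of secukinumab versus placebo is < 0.05 and the corresponding odds ratio is greater than 1", significance in favour of that dose is shown.

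SAP 5.4.1 gives the code for this analysis. The model and comparison statements are "Model AVAL= TRT MTX weight; Lsmeans TRT / diff cl exp". The response has no event option and no sort option, and the treatment comparison has no control level. The exact-logistic fallback in the same section also names no event. The variable key says only "where AVAL= dependent variable TRT= Treatment MTX= Methotrexate usage at baseline Weight= body weight".

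Other parts of the code bear on the coding:

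- The multiple-imputation code takes the response rate from "tables <response> / binomial (level=2 cl=wilson correct", and a note there says that "sometimes all responses may be imputed to 0 or 1 at a given combination of response variable".
- The Fisher fallback selects arms with "Where TRT in ('AIN457 xx mg' 'Placebo", so treatment is held as text.
- The ANCOVA contrasts in SAP 5.4.3 place placebo third of three.

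SAP 5.4.3 extends the logistic code to the secondary endpoints: "Categorical variables will be analyzed using the logistic model, using the code described above".

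**The concern.** For a two-level outcome with no event named, PROC LOGISTIC models the first level in sort order. This is known software behaviour; the documents do not state it. If non-responders sort first, the fitted odds are the odds of failing to respond. The exponentiated difference between active and placebo is then the reciprocal of the odds ratio in SAP 2.5.2.

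A rule that requires an odds ratio above 1 is sensitive to this. Applied mechanically to the inverted figure, it would fail an effective dose and could pass a harmful one. The same fragment serves the exact model and the categorical secondary endpoints. For dactylitis and enthesitis, where yes is the bad outcome, the text does not say which level is the event, so the odds ratios of different endpoints could point different ways with nothing to label them.

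**Working it through.** **1. The plan's own figures.** SAP 3 assumes 50% on 300 mg and 20% on placebo, 2:1 allocation, two-sided 0.05, power 0.90 and a continuity-corrected chi-squared test. Recomputed, this gives 88 and 44, as stated (78 and 39 without the correction). Inflating for 10% loss gives 98 and 49, which the plan rounds to 100 and 50. The stated odds ratio also reproduces: (0.5/0.5) / (0.2/0.8) = 1 / 0.25 = 4.

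**2. Which outcome level sorts first.** AVAL's coding is not given. The imputation code treats response as 0 or 1 and reads the responder proportion from level 2. On that coding non-response is level 1, the level modelled by default. No/Yes and N/Y sort the same way.

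**3. Which way the treatment difference runs.** Without a named control, the difference is taken as earlier level minus later level.

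- The text labels in SAP 5.4.1 sort AIN457 before Placebo.
- The SAP 5.4.3 contrasts, 1 0 -1 for 300 mg against placebo and 0 1 -1 for 150 mg against placebo, require placebo last.
- SAP 2.1 numbers the groups 300 mg = 1, 150 mg = 2, placebo = 3.

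All three give active minus placebo.

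**4. The odds ratio the code would print.** Odds of non-response are 0.5/0.5 = 1 on 300 mg and 0.8/0.2 = 4 on placebo. The ratio is 1/4 = 0.25.

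**5. Dependence on coding, at 50% v 20%.**

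| AVAL | TRT order | Printed odds ratio |
|---|---|---|
| response second (implied by the code) | active before placebo (implied by the code) | 0.25 |
| response second | placebo first | 4 (two inversions cancel) |
| response first | active before placebo | 4 |

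**6. Effect on the rule.** All pairs of binomial counts for 100 and 50 patients were enumerated, with an unadjusted Wald test on the log odds ratio (critical value 1.96):

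- Event = response: rule met with probability 0.960.
- Event = non-response, active minus placebo: 3.7 × 10⁻⁹.
- Event = non-response with the rates reversed (20% active, 50% placebo): 0.962.

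A simulation with the planned covariates agrees. It used 100/100/50 patients and 4,000 trials, and assumed 150 mg at 50%, methotrexate use 50%, weight mean 90 kg and SD 20, and no covariate effects. The rule was met in 96.0% of trials with response as the event and in 0.0% with non-response; the median odds ratios were 4.07 and 0.245. With rates reversed and non-response as the event, it was met in 95.8% of 1,500 trials. In every trial the two-sided p-value was the same whichever level was the event.

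**The case against.** The strongest reply is that the text governs. SAP 2.5.2 and Protocol 9.4.2 fix the estimand, the direction and the rule without ambiguity. The code is a template with placeholder dataset and dose names, and a missing option does not override the prose. This stands, and it is why the point concerns the code and not the planned analysis.

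Second, the inversion needs codings that the SAP does not state. The level-2 clue comes from a different placeholder dataset, used for the additional imputation analysis, and AVAL itself is never coded. That also stands. The further suggestion is that treatment might be coded 0, 1, 2 with placebo first, as in the hypotheses, so that two inversions cancel. This is weaker: those numbers are subscripts of the response probabilities, and such a coding would conflict with the text labels in SAP 5.4.1 and the contrasts in SAP 5.4.3. It cannot be excluded, but the SAP's code points the other way.

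Third, an inversion would be seen. SAP 2.5.2 plans responder percentages by group, and SAP 2.5.4 plans a supportive rule and confidence intervals based on responder proportions. An odds ratio of 0.25 beside 50% and 20% would be hard to miss. This is a fair limit on the practical risk, though Section 5 of the SAP is meant for later drafting of a CSR appendix, so uncorrected code could be carried forward.

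Fourth, no odds-ratio-above-1 rule applies to dactylitis or enthesitis, and their objective is the proportion of patients with the condition. Opposite directions there are a labelling matter and do not justify redefining the event as absence.

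**Conclusion.** The code in SAP 5.4.1 is under-specified. Read with the SAP's other code and the SAS default, it gives the reciprocal of the odds ratio on which the primary decision rests: 0.25 instead of 4 at the planning rates. The conclusion rests on three assumptions: 0/1 coding with response second, active arms sorted before placebo, and the software default, which was not run here.

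A reader might infer that the primary analysis is wrong as written and that an effective dose is bound to fail. The documents do not support that. They never fix the coding of AVAL in the analysis dataset, and the text states the intended direction clearly. The p-value and the sample size do not change, and the planned response rates would expose the error. The probability of about 4 × 10⁻⁹ describes literal, unchecked use of the code, not the likely conduct of the trial. This is a correction worth making because it costs almost nothing and makes the code deliver the stated rule; it does not undermine the design.

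**What to change.** In SAP 5.4.1:

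- Define AVAL=1 as responder and 0 as non-responder.
- Write `Model AVAL(event='1') = TRT MTX weight;` in both the logistic and the exact-logistic code.
- Name placebo as the control in the LSMEANS comparison, so that each odds ratio is dose over placebo whatever the sort order.
- Add a programmed check that each odds ratio agrees in direction with the raw response rates.

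In SAP 5.4.3, state the event for each categorical secondary endpoint. For dactylitis and enthesitis, use presence at Week 16, in line with the objective, and label the output so that an odds ratio below 1 is read as favouring secukinumab.

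The cost is a few words of code and one validation step. No estimand, test, sample size or data collection changes.

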2.5.4 Supportive analyses

The primary efficacy variable will also be analyzed at each time point till Week 16 for the Full Analysis Set using the Cochran-Mantel-Haenszel (CMH) test to compare secukinumab 300 mg against placebo, adjusting for methotrexate usage at baseline (yes, no) (Stokes, Davis, and Koch, 2012).

If the treatment comparison p-value is < 0.05 and the proportion of patients who are ACR20 responders is higher in a secukinumab treatment group compared to the placebo treatment group, statistical significance in favor of that dose of secukinumab is shown. Two 95% confidence intervals for the difference between each dose of secukinumab versus placebo in the proportion of patients who are ACR20 responders will be calculated using the normal approximation to the binomial distribution.

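### The ACR20 multiple-imputation template resets 100 imputations inside each existing set, and no adjusted odds ratio against placebo is specified for the imputed data

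*SAP*

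**What the plan says.** SAP 2.5.3 keeps non-responder imputation for the primary analysis and adds a multiple-imputation analysis of ACR20. The ACR components are imputed and response is then derived from them. The section says in general terms that ordinary methods may be applied to the completed sets; it names no model and no comparison.

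SAP 5.4.1 gives the detail, under missing at random:

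- Number of imputations: "Impute the missing values 100 times (NIMPUTE"). The first PROC MI call runs by arm with `nimpute=100`.
- Further components: "this step will be repeated for every components of ACR". The example for the second component takes the output of the first as input, runs "by trt _imputation_; var weight_base" and so on, and has "out=imp2 minmaxiter=10000000 nimpute=100 seed=457".
- Analysis of the completed sets: "The response rate will be calculated for each imputation and then combined using Rubin's rules". The code is PROC FREQ by arm, visit and imputation, then "proc mianalyze data=logit; by trt visit ; modeleffects lmean; stderr lse", then a back-transformation to a rate and interval.

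The other visible ACR20 inference up to Week 16 is comparative. SAP 2.5.2 reports "The odds ratios for each dose of secukinumab versus placebo, 95% confidence intervals for the odds ratios, and p-values" from a logistic model with treatment, baseline methotrexate use and body weight. SAP 2.5.4 adds a Cochran-Mantel-Haenszel test and "Two 95% confidence intervals for the difference between each dose of secukinumab versus placebo".

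**The concern.** There are two separate matters.

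The first is a contradiction. The words ask for 100 imputations. The printed call asks for 100 new imputations inside each of the sets that already exist, and does so again for each further component. A programmer has to depart from either the words or the code.

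The second is an omission. In the visible text this is the only analysis that replaces the non-responder rule with a missing-at-random assumption for ACR20. Its natural use is to show whether the 300 mg versus placebo odds ratio depends on counting missing patients as failures. What is written out stops at a rate per arm and visit, so the result cannot be set directly beside the adjusted odds ratio of SAP 2.5.2.

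What is at stake is how useful and reproducible a supportive analysis is. The primary result is not in question.

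**Working it through.** **Number of completed sets**

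Inputs from SAP 5.4.1: 100 imputations in the text; `nimpute=100` in the first call, by arm; `nimpute=100` in the second call, by arm and existing imputation; repetition for every component. SAP 2.5 lists two joint counts and five further measures, so seven components (eight if hsCRP and ESR were imputed separately).

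When each call runs inside every set left by the one before, the number of sets is the product of the NIMPUTE values.

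1. After the first component: 100. This reproduces the stated figure.
2. After the second: 100 × 100 = 10,000.
3. After k components: 100^k, so 100^7 = 10^14 for seven and 10^16 for eight.
4. With `nimpute=1` in every call after the first: 100 × 1 × … × 1 = 100. The stated figure is recovered for any number of components.

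Downstream, PROC FREQ runs by arm, visit and a single imputation index, and PROC MIANALYZE pools over that index. No second index identifies sets nested within sets. The later steps therefore fit the 100-set reading and not the nested one.

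**What is pooled**

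| | Primary (SAP 2.5.2) | Multiple imputation (SAP 5.4.1) |
|---|---|---|
| Unit of analysis | all three arms in one model | one arm at one visit |
| Covariates | methotrexate, body weight | none at this step (both are in the imputation model) |
| Quantity | odds ratio for each dose v placebo | logit of the response rate |
| Output | OR, 95% CI, p-value | rate, 95% CI |

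Some of the comparison can be recovered from the right-hand column. The arms are imputed separately, so their pooled logits are independent. An unadjusted log odds ratio is then the difference of two logits, with SE equal to the square root of the sum of the squared SEs.

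As an illustration only, take the planning values in SAP Section 3 (50% of 100 v 20% of 50) with no missing data:

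- Arm SE on the logit scale = 1/√(n p (1 − p)). For 300 mg: 1/√(100 × 0.25) = 0.200. For placebo: 1/√(50 × 0.16) = 0.354.
- Log odds ratio = ln[(0.5/0.5)/(0.2/0.8)] = ln 4 = 1.386. The odds ratio of 4 is the SAP's own figure.
- SE = √(0.200² + 0.354²) = 0.406.
- 95% CI = exp(1.386 ± 1.96 × 0.406) = 1.80 to 8.87.

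So an unadjusted contrast can be derived by hand. The adjusted one cannot, because it needs the model of SAP 2.5.2 fitted to the patient-level completed sets. Adding covariates to a logistic model changes the odds ratio being estimated, so the hand-derived figure is not the same quantity as the primary estimate.

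**The case against.** The strongest reply on the first matter is that the code is a schematic. It has blank options and placeholders, the second call is offered as an example, and the intended 100 is stated in words just above. Any programmer would notice before producing a result. That is fair, and it means no estimate is shown to be at risk. It does not make the printed call right: SAP Section 5 is meant to feed the CSR methods appendix and is the only visible detailed specification.

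On the second matter, SAP 2.5.3 follows directly after the logistic model, and its general sentence about analysing completed sets could be read as the same model under a different missing-data rule. The unadjusted contrast is also recoverable. Both points stand in part, which is why this is an omission and not an error of method. But the general sentence names no model, and where the SAP becomes specific it specifies arm rates only.

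It is also true that the SAP calls this only an additional analysis and that protocol 9.4.3 plans no multiple imputation, so no protocol commitment is broken.

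**Conclusion.** Two limited points hold in the visible text; SAP 2.13 cannot be seen. The later imputation calls contradict the SAP's own count of 100 by a factor of 100 for each further component. No covariate-adjusted contrast with placebo is specified for the imputed data, so the primary odds ratio is not directly checked under missing at random. The primary analysis, alpha and sample size are untouched.

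Three stronger readings are not supported:

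- A reader might infer that the standard errors will come out too small. If the inner copies shared one index value, each patient would be counted 100 times after two components and the arm SE would fall tenfold (0.200 to 0.020 at 50% of 100). That depends on how the software writes a duplicate index, which the documents do not show.
- A reader might infer that the analysis can say nothing about 300 mg versus placebo. The hand-derived unadjusted odds ratio shows otherwise.
- A reader might infer that the repair was, or will be, improvised after unblinding. The visible history entries postdate the Week 16 lock, but earlier pages are missing. The date of the imputation text, and whether a correct program had already run, cannot be established.

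**What to change.** 1. Keep `nimpute=100` in the first PROC MI call and set `nimpute=1` in each later call run by arm and imputation.
2. Derive ACR20 in each of the 100 completed sets. Fit the logistic model of SAP 2.5.2 (treatment, methotrexate at baseline, body weight) by imputation, and pool the log odds ratios for 300 mg v placebo and 150 mg v placebo by Rubin's rules. Both covariates are already in the imputation model, so that model need not change.
3. Report the pooled odds ratios and 95% CIs as supportive, beside the non-responder result. Keep the pooled arm rates by visit as description.
4. Enter the change with its date in the SAP history. If it is made after the Week 16 unblinding described in SAP 2.1, say so there and in the CSR. SAP Section 4, which at present lists no changes, is a suitable place for a note.

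The cost is a few lines of code and text. No new data are needed.
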